If yes, list current symptoms: _____

Suspicion of contact allergy associated with metal exposure

Type of metal exposure

- Cardiac implant (stent, pacemaker, etc.)
- Orthopedic implant (knee, hip or other)
- Gynecological implant or device
- Surgical hardware (plates, screws, wires, pins, rods, expanders, staples)
- Dental metal implant
- Dental metal appliance, prosthesis or filling
- Injection of aluminum containing vaccination
- Other _____

Other reason Investigator believes the subject qualifies for study inclusion

Past positive lymphocyte proliferation (or transformation) test to one of the dilution series metals being tested on this study

Name of metal tested: _____

Date of test: _____

Results: _____

Other _____

Figure 4: Type of Metal Exposure Questionnaire

Name of Procedure	_____	
Date of Procedure	_____	
Date symptoms first began	_____	
Patient's description of symptoms	_____	
Site(s) of onset	_____	
Symptoms currently present?	 Yes	 No
Duration	 Continuous	 Sporadic
If sporadic:	_____	
How long do symptoms last?	_____	
What is the length of time between episodes?	_____	
Other symptoms? (itching, burning, pain, etc.)	_____	
Medication Taken?	 Yes	 No
If yes:	_____	
Name of Medication	_____	
Start Date	_____	
Stop date (or ongoing)	_____	
Dose	_____	
Frequency	_____	
Route	_____	

Subjects who qualify for participation will have the investigational allergen panel(s) and reference allergens applied (with the exception of subjects enrolled in Germany who will not be tested with the reference allergens) to the paraspinal region of the upper back. Areas of contact dermatitis, uneven skin tones, tattoos, scars, moles, excessive hair or other skin disfigurement should be avoided. Upper arms may be used if there is not adequate space on the back for all panels. In summary, within these parameters, investigators will use their medical expertise to determine panel placement based on the features of each subject's back as they would normally do in clinical practice.

Panels may be further secured with medical tape (e.g., Scanpor® or patchProtect™). PatchMap may be used to document panel placement. The use of PatchMap will be required in Germany. The time of application will be documented.

The panel will be applied to the subject populations per the following:

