- Sensitive subjects (those who have had a past positive patch test to at least one of the dilution series allergens) may be tested with the allergen panels(s) and corresponding reference allergen(s) (with the exception of subjects enrolled in Germany who will not be tested with the reference allergens) to which they have had a previous response.
 - The Investigator will use his or her experience and medical expertise to determine if a subject with a past positive patch result should be tested to all dilution series allergens or only to the allergen to which the subject has had the past response.
 - Subjects with a past positive response to copper, zinc, tin, manganese or molybdenum will be tested with the panel containing the past positive response allergen plus the other allergen(s) located on the same panel. Specifically, Panel 2 contains copper, zinc and tin, and Panel 3 contains manganese and molybdenum. Hence, subjects with a past positive response to one of the allergens on the panel will also be tested with the other allergen(s) located on the same panel. It will not be necessary to test the additional reference allergens.
- Subjects with suspicion of metal contact allergy potentially associated with a metal implant will be tested with all dilution series and reference allergens.
- All subjects will be tested with the excipient controls on Panel 6. The Investigator will use his or her experience and medical expertise to determine if a subject with a strong suspicion of metal contact allergy who has not undergone previous patch testing will benefit from being patch tested with the four common allergens (nickel, chromate, cobalt and gold) in order to provide the individual with a complete diagnosis of metal contact allergy. Should the Investigator decide that testing with the four common allergens will not be of benefit to the subject, the Investigator will cut Panel 6 as illustrated in Figure 9, (Section 11.1, Investigational Allergen Panels) before applying the panel.

10.2 Visit 2: Day 2

Prior to removal of the investigational allergen and reference panels, tape adhesion will be evaluated and scored according to the following adhesion scale:

Excellent:	Skin contact good; all tape edges adherent; all allergens in contact with the skin
Good:	Skin contact acceptable; some tape edges lifting; all allergens in contact with the skin
Poor:	Little to no skin contact with panel; one or more allergens not in contact with the skin

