Detached:	Panel completely off the skin; none of the allergens in contact with the skin

If adhesion is 'Poor' or 'Detached' the allergen sites that were not in contact with the skin at the time of panel removal will be identified.

Patches that do not remain in place (completely detached) for the intended wear period (approximately 48 hours or two days) will not be replaced. The subject will be asked to return for follow-up visits until all patch sites reactions have resolved but data from this subject will not be included in the analysis of positive responses necessary to determine optimal dose.

Subjects whose patches are not worn for the intended wear period may return to be retested after 3 weeks at the discretion of the Investigator providing the skin site remains free of conditions that may affect test results.

Factors such as oily skin, excess hair, wet panel, sweat/skin moisture, and activity-associated failure, which may potentially contribute to poor adhesion, will also be captured on the data collection form.

The patch panels will be removed and time documented. There will be at least a 15-minute wait between patch removal and the irritation evaluations. Following the 15-minute wait, tape sites (entire panel minus the chip sites) then the polyester chip sites will be evaluated for skin irritation.

[figure not shown]
Skin irritation will be documented as follows:

- Panels 1-6: Irritation attributed to the adhesive used to adhere the panels to the skin (tape irritation) will be documented if the site of the entire panel with the exception of the chip sites, as shown below in Figure 5, shows signs of irritation
- Panels 1-6: Irritation attributed to the gel chips will be documented if all chip sites show signs of irritation. Note: To ensure that irritation resulting from skin contact with the polyester chip is not confused with an allergic response to a specific allergen, all of the polyester chip sites must present the same or nearly the same degree of irritation.
 - Panel 1: Chips on positions 1-4 and 7-10 will be evaluated for irritation
 - Panel 2: Chips on positions 1-12 will be evaluated for irritation
 - Panel 3: Chips on positions 1-4 and 7-10 will be evaluated for irritation
 - Panel 4: Chips on positions 1-12 will be evaluated for irritation
 - Panel 5: Chips on positions 1-4 and 7-10 will be evaluated for irritation

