11.0 INVESTIGATIONAL PRODUCT IDENTITY AND USE

11.1 Investigational Allergen Panels

Investigational T.R.U.E. TEST panels are produced, packed and labeled by the manufacturer SmartPractice Denmark, in Hillerød, Denmark. To protect tests against light and air, panels are sealed in aluminum foil opaque pouches. Panels are to be stored under refrigeration at 2-8°C (36-46°F). Products are labeled with allergen batch codes and expiration dating.

[figure not shown]
Each investigational panel consists of a 5.2 x 13.0 cm piece of surgical tape containing as many as 12 allergen patches. Although each allergen patch is assigned a 'chip number' for product identity, scoring will be by position placement as illustrated below.

Figure 7: Illustration of Position Numbering

An up arrow and two notches indicate the proper product orientation. The uppermost notch on the left side of the panel indicates the top left of the panel, the lower notch indicates the bottom of the panel. The patch chip numbering is unmistakable when the panel is removed from its pouch. Panels are to be applied with the numbers facing upright.

Figure 8: Application of Dilution Series Allergens

- Peel open package and remove test panel.
- Remove plastic covering.
- Position the panel to the paraspinal region of the upper back being careful to avoid areas of contact dermatitis, uneven skin tones, tattoos, scars, moles, excessive hair or other skin disfigurement.
- Ensure that each patch is in contact with the skin by smoothing the panel outward from the center
- Use a skin marker to indicate the location of the two notches on the panel
- Panel may be secured with additional tape, if needed.

[figure not shown]
In order to differentiate between panels once they are applied the following chip numbers are used for each panel. The *set* of numbers used is unique to each panel so that individual panels can easily be identified:

	Panel 1	Panel 2	Panel 3	Panel 4	Panel 5	Panel 6
Chip numbers	1-4 and 7-10	13-24	25-28 and 31-34	25-36	3-6 and 9-12	1, 4, 5, 7, 8, 12, 28

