Overall concordance of skin reaction responses from each allergen dose will be compared with reference allergen by using Kappa statistic as described below,

Kappa statistics (K) = $(P_0 - P_e) / (1 - P_e)$

Where P_0 is the relative observed agreement among raters (identical to accuracy), and P_e is the hypothetical probability of chance agreement and the Kappa agreement statistics score is interpreted as,

≤ 0 as indicating no agreement

0.01 – 0.20 as poor agreement

0.21 – 0.40 as fair agreement

0.41 – 0.60 as moderate agreement

0.61 – 0.80 as good agreement

0.81 – 1.00: very good agreement

Concordance will be measured using all subjects who are tested with each allergen and corresponding reference allergen.

Note: Data from the subjects with the completely detached patches for the intended wear period (approximately 48 hours or two days) will not be included in the analysis of positive responses necessary to determine optimal dose.

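### A completely detached patch removes the whole subject from the count of 15, although adhesion is graded by panel and the trigger is undefined; the analysis set for kappa is given as both mFAS and FAS

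*SAP*

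**What the plan says.** **Adhesion.** Protocol 10.2 grades each panel at Visit 2. The grade Detached means "Panel completely off the skin; none of the allergens in contact with the skin". For panels graded Poor or Detached, the individual sites without skin contact are also recorded.

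**Exclusion.** When patches are completely detached before the end of the wear period, protocol 10.2 says "data from this subject will not be included in the analysis of positive responses necessary to determine optimal dose". The Note in SAP 6.1 carries this over: "Data from the subjects with the completely detached patches for the intended wear period (approximately 48 hours or two days) will not be included" in that analysis. Protocol 11.1 describes a panel as a "piece of surgical tape containing as many as 12 allergen patches", so there a patch is one chip and not the panel.

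**Retest.** Protocol 10.2 adds: "Subjects whose patches are not worn for the intended wear period may return to be retested after 3 weeks", at the investigator's discretion. SAP 5.1 lists data from unscheduled visits and keeps them out of summary tables.

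**Dose rule.** Under SAP 6.1 the selected dose is the lowest one with positive responses in at least 15 subjects, scored by position. Kappa against the reference allergen is the second primary endpoint. It leaves out Germany, and subjects with a missing investigator determination on either panel. Under protocol 10.6, a site with no positive score at any assessment visit is categorised as negative.

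**Analysis sets.** SAP 3.6.2 puts all efficacy analysis on mFAS. The primary-endpoint row in SAP 7 names kappa and FAS. SAP 3.7 requires mFAS subjects to meet every eligibility criterion; the definition in 3.6.2 does not.

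**The concern.** The texts use three units: the grade belongs to a panel, the trigger is a patch, and what is removed is the subject's data. A subject with suspected metal allergy is tested with all dilution series, which fill investigational Panels 1 to 5, and also wears control Panel 6 and, outside Germany, the reference panels. If the vanadium panel comes off, the literal rule also discards that subject's valid aluminum, copper and titanium readings.

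The trigger is open as well. Neither document says whether one chip, one panel or all panels must be lost, or whether losing Panel 6 or a reference panel counts. Two programmers could both follow the Note and obtain different counts. Because the rule is a fixed integer threshold, and the protocol calls sensitization to these metals rare, one or two lost positives can change which dose is selected or leave none selected.

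The kappa analysis has two related gaps. A site on a detached panel may default to negative under protocol 10.6 instead of being treated as missing. And kappa is assigned to two analysis sets.

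**Working it through.** **The plan's own figure.** SAP 3.3 derives a past minimum of 14 positives from 70-90% of 20 subjects: 0.70 × 20 = 14, which reproduces and is not in dispute. The quota of 15 and the cap of 400 have no stated derivation, and no detachment rate is given.

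**Inputs.** From the documents: threshold 15; five investigational panels for a subject tested with everything. Assumed: detachment probability q = 0.5%, 1% or 2% per panel; every positive subject wears all five panels; only investigational panels count as triggers.

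**Step 1. Chance that a valid positive is lost.** This is the chance p that at least one of the other four panels detaches, given that the panel carrying the positive stayed on.

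- Independent panels: p = 1 − (1 − q)^4 = 0.0199, 0.0394, 0.0776.
- Clustered within subject (beta-binomial, correlation ρ = 0.3): a = q(1/ρ − 1), b = (1 − q)(1/ρ − 1), p = 1 − Π(b + j)/(a + b + j) for j = 1 to 4. At q = 1%, a = 0.0233 and b = 2.31, so p = 1 − (3.31/3.333)(4.31/4.333)(5.31/5.333)(6.31/6.333) = 0.0203. At 0.5% and 2%, p = 0.0102 and 0.0403.

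**Step 2. Chance that the count falls below 15.** With n valid positives, it is P(X ≥ n − 14), where X is Binomial(n, p). For example, with n = 16, q = 1% and independence: 1 − 0.9606^16 − 16 × 0.0394 × 0.9606^15 = 0.129.

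| Valid positives | Clustered, q = 0.5% / 1% / 2% | Independent, q = 0.5% / 1% / 2% |
|---|---|---|
| 15 | 14% / 26% / 46% | 26% / 45% / 70% |
| 16 | 1% / 4% / 13% | 4% / 13% / 36% |
| 20 | under 0.1% throughout | at most 0.3% |

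**Step 3. Sensitivity.**

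- If losing Panel 6 also excludes the subject (five other panels in place of four), n = 16 gives 1%, 5% or 17% clustered and 6%, 18% or 46% independent.
- A past-positive subject tested on one investigational panel has no other investigational panel to lose. If 8 of the 16 are such subjects, X is Binomial(8, p), and P(X ≥ 2) under independence is 1%, 4% or 12%.
- With panel-level exclusion, the loss caused by other panels is 0.

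**Step 4. Analysis sets, side by side.** The count of 15 has no row in SAP 7, so it falls under the general statement in 3.6.2 and its set is mFAS. Kappa has a row, and that row says FAS. A subject with no readings adds nothing to either analysis. The sets therefore give different results only through subjects who fail an eligibility criterion but have readings: they are in under FAS and under the 3.6.2 definition, and out under 3.7.

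**The case against.** A reader might infer that the protocol and SAP contradict each other on the extent of the exclusion. They do not: both remove the subject's data. What is unclear is the trigger.

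Subject-level exclusion can also be defended. The listed causes of poor adhesion, "Factors such as oily skin, excess hair, wet panel, sweat/skin moisture, and activity-associated failure", are mostly features of the subject, so a subject who loses one panel may have had weaker contact elsewhere. This stands as a reason for a sensitivity analysis. It does not justify discarding panels whose own grade shows good contact. The same clustering makes the lower column of results the more plausible one.

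The size rests on assumptions. Extra fixation is allowed ("Panels may be further secured with medical tape"), and retests can recover readings. For past-positive subjects the investigator decides whether they "should be tested to all dilution series allergens or only to the allergen to which the subject has had the past response", so some wear few panels. All of this lowers the figures.

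A reader might also infer that the count of 15 could be run on either FAS or mFAS. The text does not support that, since 3.6.2 already covers the count.

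Two gaps are partly filled elsewhere. SAP 5.1 might govern retest readings if a retest is an unscheduled visit, and the Note might extend to kappa, because SAP 4.1 lists kappa under determination of the optimal dose. Neither is stated, and the first would keep valid retest readings out of the summary tables.

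**Conclusion.** The point holds in two parts.

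(a) Followed literally, the detachment rule discards valid readings from adherent panels, and its trigger is undefined. It matters for doses at or just above 15 positives and hardly at all by 20. The percentages assume 0.5-2% detachment per panel and five panels for every positive subject, and the clustered column also assumes a correlation of 0.3. None of these comes from the documents, so the true size is unknown. The wording defect is certain; a changed dose is only possible.

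(b) The SAP gives kappa two analysis sets and gives mFAS two definitions. The effect is limited to ineligible subjects who have readings, and their number is unknown.

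**What to change.** Reword the SAP 6.1 Note, with a matching clarification of protocol 10.2 or an entry in SAP 3.5:

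- Exclude from the count only the readings from the detached panel, and keep the subject's other panels.
- State that losing Panel 6 or a reference panel does not remove investigational readings from the count of 15.
- For kappa, drop any pair in which either site was on a detached panel, or was recorded as out of contact on a panel graded Poor, so that it does not default to negative under protocol 10.6.
- State that readings from a retest the protocol permits replace the detached panel's readings and are not unscheduled data under SAP 5.1.
- Change the SAP 7 primary row to mFAS, add the count of 15 to it, and use one mFAS definition in 3.6.2 and 3.7.

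The cost is a few sentences before database lock and a merge with the panel grades and site records that protocol 10.2 already collects. The downside is that readings are kept from subjects whose other panels may have had weaker contact, or who lost the controls. Report how many there are, and show the subject-level exclusion as a sensitivity analysis.

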6.2 Secondary Endpoint Analysis

Frequency and percentage analysis will be carried out for below mentioned endpoints for investigational and reference allergen to obtain the safety of allergen.

Determination of allergen safety:

- Frequency of tape and polyester chip induced irritation or allergic reactions at Visits 2 through 6.
- Frequency of subject reported sensations of itching and/or burning for each allergen panel at patch removal.
- Frequency of positive (1+, 2+, 3+) skin reaction will be tabulated for the each investigational and reference allergen dose tested.
- Frequency of negative, doubtful, irritant, late and persistent skin responses for each investigational and reference allergen dose at each post removal visit (late and persistent reactions at visits 4, 5 and 6 only).
- Frequency of all adverse events. This will be brief in the section 6.2.1.

STATISTICAL ANALYSIS PLAN

Date : 30 NOV 19

Version: 01

Product Name:

Sponsor Study No.: SP 14 8MP 201 Metal Allergen Epicutaneous Patch

6.2.1 Overall Summary of AEs or TEAEs

Adverse Events (AEs) will be coded using the Medical Dictionary for Regulatory Activities (MedDRA) dictionary Version 20.0.

This table will include the number of events (Adverse Events or Treatment Emergent Adverse Events), number and percent of subjects who experienced,

- AEs or TEAEs
- Serious AEs or TEAEs
- Related AEs or TEAEs (i.e. Relationship to study panel)
- AEs or TEAEs leading to study discontinuation

6.2.2 Summary of AEs or TEAEs by SOC and PT

A summary of number and percent of subjects who experienced at least one AE or TEAE as well as the number of events, number and percent of subjects who experienced each specific SOC and PT will be presented.

If a subject has more than one occurrence of the same preferred term (PT) for an AE then the PT will be counted only once for that subject under the SOC at which it was experienced.

In case AE start date is missing then “Date of randomization” will be considered for start date and if the stop date is missing then “Date of last contact” is considered for AE duration calculation.

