7.0 OBJECTIVE

To evaluate the diagnostic performance and safety of metal allergens proposed for inclusion in Metal Panel T.R.U.E. Test. The study will compare the diagnostic performance (primary) and safety (secondary) of ascending patch test doses of aluminum, copper, manganese, molybdenum, tin, titanium, vanadium and zinc allergens.

To determine if subjects who have not had previous patch testing are allergic to any of the most common metal allergens; nickel, cobalt chromium and gold.

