7.2 Secondary Endpoint

Determination of allergen safety

- Frequency of tape and polyester chip induced irritation or allergic reactions at Visits 2 through 6.

- Frequency of subject reported sensations of itching and/or burning for each allergen panel at patch removal.
- Frequency of positive (1+, 2+, 3+) skin reactions for each investigational and reference allergen dose at each post removal visit and overall.
- Frequency of negative, doubtful, irritant, late and persistent skin reactions for each investigational and reference allergen dose at each post removal visit (late and persistent reactions at visits 4, 5 and 6 only).
- Frequency of all adverse events. Documentation for all local and systemic adverse reactions classified by the investigator as possibly or definitely related to the study product (e.g., erythema, hyper-pigmentation, hypo-pigmentation, skin thinning or dermatitis flare) will include grade (mild, moderate or severe) and time point (clinic visit).

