5.1 General Considerations

General considerations are as follows:

- Unless otherwise specified, all statistical tests will be performed using a 2-sided, 0.05 significance level.
- Descriptive statistics such as n, mean, median, standard deviation (SD) and range (minimum, maximum) will be used for summarizing the continuous variables. Frequencies and percentage frequency will be computed for categorical data.
- The summaries will be sorted by visits and allergen. Listings will be sorted by subject number and visit.
- Unscheduled visits data, will be listed only. Summary tables will not utilize the unscheduled data.
- All statistical analysis will be performed using SAS®, Version 9.4 or higher (SAS Institute Inc., NC Cary, USA).

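### Local adverse events outside the skin scores cannot be compared by dose, because no patch position is required for them and no adverse event table is split by allergen or dose

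*SAP*

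**What the plan says.** Safety by dose is an aim of the trial. Protocol 7.0 states: "The study will compare the diagnostic performance (primary) and safety (secondary) of ascending patch test doses of aluminum", followed by the other seven metals. SAP 2.1 repeats it.

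For related local and systemic reactions, Protocol 7.2 asks for documentation that "will include grade (mild, moderate or severe) and time point (clinic visit". Protocol 4.8 and 12.1 and SAP 4.2 ask for the same two items. None of them names panel, position, chamber or dose.

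SAP 6.2 opens by promising frequencies for both investigational and reference allergens, over a list that includes adverse events. SAP 5.1 adds: "The summaries will be sorted by visits and allergen". The adverse event subsections do not carry this through:

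- SAP 6.2.1 is an overall summary. Its causality line reads "Related AEs or TEAEs (i.e. Relationship to study panel".
- SAP 6.2.2 gives subjects with any event, "as well as the number of events, number and percent of subjects who experienced each specific SOC and PT will be presented". A term repeated within a subject counts once in the subject column: "then the PT will be counted only once for that subject under the SOC at which it was experienced".

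Skin reactions are handled differently. Under Protocol 11.1, "scoring will be by position placement as illustrated below". Under SAP 6.2, the frequency of positive "skin reaction will be tabulated for the each investigational and reference allergen dose tested". Negative, doubtful, irritant, late and persistent responses are also tabulated for each dose.

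**The concern.** Doses are compared within the subject. Anyone given a series wears all of its doses at once, so no group of subjects received only the low dose or only the high dose. A subject-level adverse event rate therefore says nothing about dose. Only the site of the event can do that.

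For events that the reaction score covers, the site is recorded. For events that it does not cover, the adverse event record is the only planned source, and the documents do not require it to hold the site. Protocol 7.2 itself names pigment change and skin thinning as examples of related reactions. Protocol 13.6 lists scarring, keloids and infection, as well as severe pigment change or itching at a test site that outlasts day 21, which falls after the usual last reading.

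At stake is the dose comparison, and the comparison with the reference, for this class of local events. They may be few, but they bear on the choice between two doses that elicit similar numbers of positive reactions.

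**Working it through.** The documents give no figure for this point, so there is nothing to reproduce. The check has three parts.

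**1. What the score covers.** Protocol 10.3.2 scores erythema, infiltrate, papules, vesicles, bullae and irritant reactions. Protocol 10.4.2 and 10.5 score negative or 1+ to 3+ at Visits 4 to 6. Pigment change, skin thinning, scarring and infection have no grade on this scale, so the by-dose tables in SAP 6.2 cannot show them. Itching and burning are recorded per panel at removal, not per patch.

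**2. How many sites share one count.** The inputs are the panel tables in Protocol 11.1 and the reference list in 11.2.

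- Dose patches: 8 + 12 + 8 + 12 + 8 = 48.
- Panel 6: 3 controls, plus 4 common allergens at the investigator's discretion.
- Reference chambers: aluminum 2, copper 1, manganese 1, molybdenum 1, tin 1, titanium 4, vanadium 2, zinc 1 = 13.

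| Subject | Sites worn |
|---|---|
| Suspected allergy, outside Germany | 48 + 13 + 3 = 64; with common allergens 68 |
| Suspected allergy, Germany (no references) | 48 + 3 = 51; with common allergens 55 |
| Past positive, tested to aluminum only | 8 + 2 + 3 = 13; in Germany 8 + 3 = 11 |

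In the 68-site case, 48/68 = 71% of sites are investigational doses and 13/68 = 19% are references. A subject tested only to aluminum wears 8/48 = 17% of the dose patches. Safety is analysed on all randomized subjects, so one percentage mixes people with very different exposure and is not the denominator for any single allergen.

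**3. What the planned table can distinguish.** Suppose n of 400 subjects have one local PT within a four-dose series. The 400 is the planned total; n is an assumption, as is every subject wearing that series. The planned table shows n/400 of subjects whatever the pattern across doses.

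| Pattern | Rate per dose | n = 4 | n = 20 | n = 40 | Events if each site is logged |
|---|---|---|---|---|---|
| All at top dose | 0, 0, 0, n/400 | top 1.00% | top 5.00% | top 10.00% | n |
| One site each, spread evenly | n/1600 each | 0.25% | 1.25% | 2.50% | n |
| All four sites in each subject | n/400 each | 1.00% | 5.00% | 10.00% | 4n |

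With n = 20 the table reads 5.00% in all three rows. The event total separates the third row (80 events) from the first two (20 each). It cannot separate the first from the second, and that is the contrast that bears on dose.

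**The case against.** The strongest reply is that the plan already compares local safety by dose where it matters most. Positive, doubtful, irritant, late and persistent reactions are scored by position and tabulated for each investigational and reference dose. Suspected sensitization is largely covered as well, because a new positive seen at an in-office Visit 6 is scored at its site. This stands. A reader might infer that no adverse event can be tied to a dose; the documents do not support that.

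Four further inferences also go too far.

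- *The once-per-subject rule removes the dose.* It is the ordinary rule for subject incidence, and SAP 6.2.2 reports the number of events beside it. The loss comes from the unrequired site and the unsplit table.
- *Every subject wears every dose and reference.* Protocol 10.1 lets past-positive subjects receive selected panels and waives the extra references on shared panels. Subjects in Germany receive no references.
- *The adverse event form has no place for the site.* The form and the mock tables are not among the documents. Asking for grade and visit sets a minimum and does not exclude a site entry.
- *Reference reactions are charged to the investigational product.* SAP 6.2.1 speaks of the study panel, and Protocol 10.2 numbers the chamber panels 7 and 8. Nothing limits the term to investigational patches.

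It can also be said that the general sorting rule in SAP 5.1 and the opening of SAP 6.2 already commit to a split by allergen. But the adverse event subsections do not apply it, the sorting rule stops at allergen and does not reach dose, and neither can be applied without the site.

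**Conclusion.** The point holds in a limited form. Local adverse events outside the position-scored reactions (pigment change, skin thinning, scarring and site infection, for example) cannot be compared between doses, or against the reference, with the data requirements and tables now specified. It does not extend to scored reactions. Systemic events and dermatitis flares could not be assigned to one dose even if a position were recorded.

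Between 11 and 68 sites per subject feed one undivided count. How many such events will occur is not stated, so the practical weight depends on an unknown rate. Whether the missing piece is only a table, or also the underlying data, depends on an adverse event form that is not in the documents. Because the affected comparison is part of a stated objective and the remedy is small, the change should be made before database lock.

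**What to change.** 1. Require panel and position, or reference chamber, for each adverse event at a patch site. If the adverse event form already holds a site description, code from that. If not, add a field or query the sites before database lock.
2. Add one table to SAP 6.2.2: related local events by compound and dose, reference and control. Count a subject once per patch for a given term, with the subjects who wore that patch as denominator. Positions on Panels 1 to 5 are decoded with the existing randomization key; Panel 6 is not randomized.
3. Leave the SOC/PT tables and their once-per-subject rule as they are for all events, and state that systemic events and flares are not assigned to a dose.

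The cost is one extra table. SAP 1 says the plan is finalized before database lock, so the table can be prespecified. If the site was never captured, there is also a round of data queries. The study was due to start in 2016 and the SAP is dated November 2019, so some answers may not be recoverable; the table should show those events in a row for unknown site.
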